Pfizer-BioNTech BNT162b2 (original monovalent) COVID-19 Vaccine (Comirnaty[®]) was previously approved by the FDA for individuals aged 16 years and older in a series of 2 doses administered 3 weeks apart (FDA, 2023). Pfizer-BioNTech original monovalent COVID-19 Vaccine was also previously authorized for emergency use by the FDA in individuals aged 6 months through 4 years in a series of 3 doses, with the first and second doses administered 3 weeks apart and the second and third doses administered at least 8 weeks apart; and in individuals aged 5 to 15 years in a series of 2 doses administered 3 weeks apart (FDA, 2023). Additionally, in individuals aged 5 years and older with certain types of immunocompromising conditions, a third dose in the primary series, to be administered at least 28 days after the second dose was previously authorized (FDA, 2023). A summary of FDA emergency use authorization (EUA) and full approval for primary series vaccination with Pfizer-BioNTech original monovalent COVID-19 Vaccine is provided below.

- On 11 December 2020, the Pfizer-BioNTech original monovalent COVID-19 Vaccine was authorized for emergency use in a 2-dose series by the FDA to prevent COVID-19 in individuals aged 16 years or older (FDA, 2023). On 12 December 2020, the Advisory Committee on Immunization Practices (ACIP) issued an interim recommendation (which the CDC Director endorsed) for use of the vaccine in individuals aged 16 years and older (Oliver et al., 2020).
- On 10 May 2021, Pfizer-BioNTech original monovalent COVID-19 Vaccine was authorized for emergency use in children aged 12 to 15 years in a 2-dose series in the US (FDA, 2023), and on 12 May 2021, the ACIP issued an interim recommendation for the use of the vaccine in children aged 12 to 15 years (Wallace et al., 2021).
- On 23 August 2021, Pfizer-BioNTech original monovalent COVID-19 Vaccine (Comirnaty[®]) was fully approved by the FDA for the prevention of COVID-19 in individuals aged 16 years and older (FDA, 2021). On 30 August 2021, the ACIP revised its interim recommendation (which the CDC Director adopted) to a standard recommendation for use of Pfizer-BioNTech original monovalent COVID-19 Vaccine in individuals aged 16 years and older for the prevention of COVID-19 (Dooling et al., 2021).
- On 12 August 2021, the FDA authorized emergency use of the Pfizer-BioNTech original monovalent COVID-19 Vaccine as a third dose in a primary series at least 28 days

PFIZER CONFIDENTIAL

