8.7.3. Sensitivity analysis

8.7.3.1. Exposure misclassification

During the early stages of the roll out of COVID-19 vaccines, many vaccinations may have occurred outside traditional medical care settings without reimbursement from health insurers. The potential for lack of recording of COVID-19 vaccines in claims and electronic health records may lead to misclassification of exposed individuals as "unexposed" individuals, which will underestimate vaccine coverage rates and bias comparative risk estimates for the cohort design with concurrent unexposed individuals as comparators. To address this potential bias in comparative risk estimates, sensitivity analysis will be performed using a SCRI design. Additional sensitivity analyses will incorporate a cohort design with historical unexposed comparators for pregnancy and birth outcomes.

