8.7.3.2. Self-controlled risk interval design

Sensitivity analyses incorporating a SCRI design will be implemented for outcomes with an acute onset and short risk intervals (i.e., risk intervals no longer than 42 days; specific outcomes to be indicated in the SAP) in the overall study population, in pregnant women, in immunocompromised individuals, and in individuals with a history of COVID-19. The SCRI design will not be considered for pregnancy safety outcomes. Only vaccinated individuals will be included in the SCRI analysis; the rate of a specific safety event in a post-vaccination risk interval will be compared with that in a control interval within the same individual.

For the primary series analysis, the risk interval will combine person-time in the risk intervals after the first dose, after the second dose, and after the third dose (if applicable).

PFIZER CONFIDENTIAL CT24-WI-GL02-RF02 3.0 Non-Interventional Study Protocol Template For Secondary Data Collection Study 20-May-2021 Page 96 of 120 The control interval will be outcome specific, with the duration and timing relative to vaccination specified in more detail in the SAP. Control intervals will be defined during specific periods following vaccination (up to a maximum of 183 days); to avoid bias due to healthy vaccinee effects, pre-vaccination periods will not be used. A washout period between the risk and control intervals may be incorporated for safety events for which the risk interval is not well characterized.

Because of the self-controlled nature of the design, bias of comparative risk estimates arising from differences in the distribution of time-constant confounding factors between vaccinated and unvaccinated individuals is avoided with the SCRI design. Furthermore, as the design only includes vaccinated individuals, it avoids the potential for misclassification of unexposed status due to incomplete capture of COVID-19 vaccinations in data from claims or electronic health records.

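### The SCRI's stated protection against incomplete vaccine capture does not cover people with a recorded dose and an unrecorded later dose

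*Protocol*

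**What the plan says.** Protocol Section 8.7.3.1 gives the reason for the SCRI. Early in the roll-out, "many vaccinations may have occurred outside traditional medical care settings without reimbursement from health insurers", so vaccinated people may be taken for unvaccinated comparators. The remedy follows: "To address this potential bias in comparative risk estimates, sensitivity analysis will be performed using a SCRI design".

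Section 8.7.3.2 sets out the design:

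- Who enters: "Only vaccinated individuals will be included in the SCRI analysis".
- Risk time for the primary series: "the risk interval will combine person-time in the risk intervals after the first dose, after the second dose, and after the third dose" (where a third dose applies).
- Control time: "Control intervals will be defined during specific periods following vaccination (up to a maximum of 183 days"), and "pre-vaccination periods will not be used". Duration and timing are left to the SAP. A washout is optional, for events whose risk interval is poorly known.
- Stated benefit: because only vaccinated people are included, "it avoids the potential for misclassification of unexposed status due to incomplete capture of COVID-19 vaccinations".

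Sections 8.1, 8.3.1 and 8.9 say the SCRI may become the primary design if exposure capture proves incomplete. The SCRI limitations listed in Section 8.9 are slow onset, long risk intervals and uncertain risk periods. Unrecorded later doses are not among them.

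**The concern.** In a self-controlled design, unexposed status belongs to person-time as well as to persons. Requiring a recorded dose removes the vaccinee who left no record at all. It does not remove the person whose first dose produced a claim and whose second was given at a site that sent none.

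Because all control time follows vaccination, it lies where further doses fall due. Section 6 describes the primary series for ages 16 and over as given "in a series of 2 doses administered 3 weeks apart", and a booster from 5 months after the primary series since January 2022. Both fall inside 183 days. An unrecorded dose there adds its own excess events to the control count.

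The SCRI is the named fallback when capture is poor, and poor capture is when partly recorded series are likely to be more common. Missed exposure can also dilute the concurrent cohort RR, so two low estimates that agree would not by themselves show that capture was harmless. A SAP author who relies on the sentence as written has no prompt to place control days away from the next dose.

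**Working it through.** **The plan's own figure.** The protocol states no figure for the SCRI. Its worked precision figure in Section 8.5 is for the cohort: 92% probability that the upper 95% limit is below 2.5 for myocarditis/pericarditis, with 5,000,000 vaccinated, 2 doses each, 10 per 100,000 person-years, a 21-day window and true RR 1.4.

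- Expected unexposed events: 5,000,000 × 2 × 21/365.25 × 10/100,000 = 57.5. Exposed: 1.4 × 57.5 = 80.5.
- Φ[(ln 2.5 − ln 1.4)/√(1/57.5 + 1/80.5) − 1.96] = 0.919.

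It reproduces, and this point does not affect it.

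**Inputs for the SCRI check**

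- Risk window for myocarditis/pericarditis: days 1–21 (Table 8).
- Dose 2 three weeks after dose 1 (Section 6). A dose 2 on day 21 has its risk window on days 22–42, just outside the window of dose 1.
- Latest possible control day: 183 (Section 8.7.3.2). Days 22–183 are 162 days.
- True RR: 1.4 (the Section 8.5 example) and 2.4 (illustrative; Section 6 cites 2.4 for this vaccine over 7 days at ages 12–39, 95% CI 0.4–24.9).
- Assumed, because the documents give neither: q, the share of SCRI participants with an unrecorded later dose whose window falls in the control interval (5% to 50%), and C, the control-interval length (21 to 162 days).

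**Formula.** Let f = 21/C be the share of an affected person's control interval covered by the unrecorded dose's window. The control rate is raised by the factor 1 + q·f·(R − 1), so

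expected RR = R / [1 + q·f·(R − 1)].

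| C (days) | f | True RR | q = 5% | q = 20% | q = 50% |
|---|---|---|---|---|---|
| 21 | 1.00 | 1.40 | 1.37 | 1.30 | 1.17 |
| 21 | 1.00 | 2.40 | 2.24 | 1.88 | 1.41 |
| 42 | 0.50 | 1.40 | 1.39 | 1.35 | 1.27 |
| 42 | 0.50 | 2.40 | 2.32 | 2.11 | 1.78 |
| 162 | 0.13 | 1.40 | 1.40 | 1.39 | 1.36 |
| 162 | 0.13 | 2.40 | 2.38 | 2.32 | 2.20 |

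For example, with C = 21 and q = 20%: 1.40/(1 + 0.2 × 0.4) = 1.30 and 2.40/(1 + 0.2 × 1.4) = 1.88. A Poisson simulation of three settings agreed.

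**Direction.** At R = 1 the denominator is 1 and there is no bias. Below 1 the pull is upward: 0.70 becomes 0.70/(1 − 0.2 × 0.3) = 0.74 at q = 20%, f = 1.

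**Unequal doses.** Section 6 cites 12.6 cases per million second mRNA doses against 4.4 per million first doses in the 21 days after vaccination at ages 12–39. If the recorded dose has RR 1.4 and the unrecorded dose 2.4, with q = 30% and f = 1, the expected RR is 1.4/(1 + 0.3 × 1.4) = 0.99.

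**What is not affected.** An unrecorded first dose followed by a recorded second does not enter post-vaccination control time.

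**The case against.** The protocol mostly uses unexposed status to mean that vaccinated people are taken for unvaccinated comparators (Sections 8.1, 8.3.1, 8.7.3.1). The disputed sentence gives restriction to vaccinated people as its reason, and in that sense it is true. The placement of control time, which decides how much bias arises, is properly left to the SAP; 183 days is a ceiling, not the chosen interval. All of this stands. What remains is that the sentence carries no such limit and Section 8.9 does not supply one.

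A reader might infer that the SCRI would lose a third or more of a true RR. The documents do not support that. The cited 2.4 is a 7-day ratio with a very wide interval. If the excess lasts only 7 days, then at q = 20% and C = 21 the multiplier is 1/(1 + 0.2 × 7/21 × 1.4) = 0.91; with C = 162 it is 0.99. Large losses need a short control interval starting near day 22 or a large share affected, and the protocol specifies neither.

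A reader might also infer that the SCRI is worse than the cohort when capture is poor. Nothing in the documents allows that comparison: the cohort also takes in never-recorded vaccinees as comparators. Nor is the SCRI the only response. Existing registry linkages are already used, and further linkage is named as an option (Section 8.3.1).

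Two tempting remedies fail. Restricting the main SCRI to people with both doses recorded conditions on a later exposure: someone whose event after dose 1 led them to forgo dose 2 is dropped, which biases the dose 1 RR downward. Ending control time at the earliest authorised further dose leaves almost nothing for immunocompromised people, for whom Section 6 gives a third dose from 28 days after dose 2. That is days 22–27, or 6 days, for a 21-day window, and none for 28- or 42-day windows.

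**Conclusion.** The point holds as one of unqualified wording and a missing limitation in a design with a fallback role. The SCRI removes misclassification of people with no recorded dose. It does not remove misclassification of control time in people with a recorded dose and an unrecorded later one.

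The expected effect ranges from negligible (long control interval, few people affected, or a later dose with no effect) to material (a 21-day control interval near day 22, where 2.40 falls to 1.88 at q = 20%). With equal effects by dose the pull is toward 1; it can pass 1 only if the unrecorded dose carries the higher risk. These sizes rest on assumed q and C, dose 2 on day 21 and a uniform excess over 21 days. They do not show that the SCRI as finally specified will be seriously biased.

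**What to change.** 1. In Section 8.7.3.2, limit the sentence to vaccinated people with no recorded dose.
2. In Section 8.9, add partial capture to the SCRI limitations: an unrecorded later dose can be counted as control time, with the direction shown above. This matters because the SCRI is the named fallback when capture is poor.
3. Keep all eligible vaccinees in the main SCRI.
4. For people whose recorded series is incomplete, exclude from control time the risk window that the next dose would have if given on schedule, or do so as a sensitivity analysis. Doses given off schedule will escape this, hence item 5.
5. Report SCRI results by number of recorded doses, and in registry-linked people where linkage already exists. The split by recorded doses is a diagnostic: the group with one recorded dose mixes people with an unrecorded second dose and people who stopped after an event.

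The cost is two wording changes, a few extra tables and some control days. With control days 22–183 and a 21-day window, an affected person keeps 162 − 21 = 141 days. A short control interval lying wholly on days 22–42 would have to move for these people.

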8.7.3.3. Cohort design with historical unexposed comparators (pregnancy and birth outcomes)

If feasible, a cohort design with historical unexposed individuals as comparators will be used to assess pregnancy and birth outcomes. For the cohort design with historical unexposed comparators, the comparator cohorts will be identified and followed in a time period before the introduction of COVID-19 vaccines. Exposed and unexposed individuals will be matched on maternal age and estimated pregnancy start, using similar methods as for the cohort design with concurrent unexposed comparators in pregnant women.

The use of historical unexposed individuals as comparators avoids the potential for misclassification of unexposed status due to incomplete capture of COVID-19 vaccinations in data from claims or electronic health records. The feasibility of this analysis will depend on the absence of trends in coding for each pregnancy outcome of interest over time in the historical comparator period and the study period. Further details on the composition of the cohorts, methods to address confounding, and criteria used to determine whether this design is feasible will be specified in the SAP.

8.7.3.4. Risk intervals

8.7.3.5. Outcome misclassification

Misclassification of outcome events may result in bias of the estimated effect measure estimates, particularly if the misclassification is differential between exposure groups. Quantitative bias analysis will be implemented to correct comparative risk estimates of myocarditis/pericarditis in individuals aged 12 years and older for differential outcome misclassification (i.e., positive predictive value and sensitivity) by exposure status. Details will be provided in the SAP.

8.7.3.6. Pfizer-BioNTech original monovalent COVID-19 Vaccine risk intervals

The study design approach proposed in this protocol requires that risk intervals be specified correctly. If risk intervals are too long, comparative risk estimates may be attenuated.

PFIZER CONFIDENTIAL CT24-WI-GL02-RF02 3.0 Non-Interventional Study Protocol Template For Secondary Data Collection Study 20-May-2021 Page 97 of 120 Sensitivity analysis of myocarditis/pericarditis will be conducted using alternative risk interval definitions of 1-7 and 1-14 days.

[figure not shown]
For other safety events of interest for which the risk intervals are not well characterized (to be defined in the SAP), descriptive analyses of the timing of events relative to vaccination will be conducted. If they are identified, temporal clusters will be used to define alternative risk intervals that will be used in sensitivity analyses.

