8.5. Study size

The size of the exposed population will depend on the use of Pfizer-BioNTech original monovalent COVID-19 Vaccine, and the size of the comparator population will depend on the proportion of the source population that comprises unvaccinated individuals (or individuals not receiving a third dose) over time in the data sources. The precision of comparative risk estimates will depend on the background rate and the duration of the risk interval for each safety event of interest.

Assuming a matching ratio of 1:1 for analysis of the primary series, Table 9 presents the probability that the upper limit of the 95% CI for the observed RR will be below 1.5, 2.0, 2.5, and 3.0 for assumed true RRs of 1.0, 1.2, 1.4 and study sizes ranging from 500,000 to 20,000,000 vaccinated individuals (1,000,000 doses to 40,000,000 doses, under the assumption that each individual will receive 2 doses). The estimates in Table 9 reflect a cohort analysis. These estimates are presented to cover a range of safety events of interest with respect to rareness, based on background rates in the general population.

For example, for myocarditis/pericarditis, with 5,000,000 exposed individuals and an estimated background rate of 10 per 100,000 person-years, we estimate a 92% probability that the upper bound of the observed RR would be below 2.5 assuming a 1:1 ratio between vaccinated and comparator person-time and that the true RR is 1.4.

Assumed true RR	Safety event of interest	Estimated back- ground rate per	Number of individuals vaccinated	Probability that the upper confidence limit of RR will be below the following thresholds ^a :				
		100,000 person- years (Black et al., 2021; Gubernot et al., 2021)		1.5	2.0	2.5	3.0	
1.0	Myocarditis/ pericarditis		1	500,000	0.04	0.06	0.07	0.09
		2,	1,000,000	0.05	0.08	0.10	0.13	
			2,500,000	0.07	0.13	0.19	0.26	
			5,000,000	0.10	0.22	0.34	0.46	
			10,000,000	0.16	0.38	0.59	0.75	
			20,000,000	0.28	0.65	0.87	0.96	
1.0	Myocarditis/ pericarditis		500,000	0.10	0.22	0.34	0.46	
			1,000,000	0.16	0.38	0.59	0.75	
		2.	2,500,000	0.34	0.75	0.94	0.99	
			5,000,000	0.59	0.96	1.00	1.00	
		10	10,000,000	0.87	1.00	1.00	1.00	
			20,000,000	0.99	1.00	1.00	1.00	

Assumed true RR	Safety event of interest	Estimated back- ground rate per 100,000 person- years (Black et al., 2021; Gubernot et al., 2021)	Number of individuals vaccinated	Probability that the upper confidence limit of RR will be below the following thresholds ^a :				
				1.5	2.0	2.5	3.0	

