8.7.2.2. Measures of association

For comparative analyses of general safety events, Cox models or Poisson regression will be used to estimate RRs and 95% CIs within the matched cohorts. For pregnancy outcomes, hazard ratios and 95% CIs will be estimated using Fine-Gray subdistribution proportional hazards models (using gestational age as the time scale) to account for competing risks of other end-of-pregnancy events (e.g., termination, stillbirth) (Fine JP and Gray RJ, 1999).

For comparative analysis of small size for gestational age and major congenital malformations, modified Poisson regression (Zou, 2004) will be used to estimate prevalence ratios and 95% CIs within the matched cohorts.

For the dose 1 comparative risk estimation for general safety events and pregnancy outcomes, when a second dose of vaccine is administered before the risk interval following dose 1 is complete, the risk interval will be truncated at the time of dose 2, and FU after dose 2 will be excluded from the dose 1 risk estimation. In this situation, for the dose 2 comparative risk estimation, the risk interval will start on the date of the second vaccine dose and will extend for the duration of the risk interval for dose 2.

Similarly, for dose 2 comparative risk estimation for general safety events and pregnancy outcomes, when a third dose of vaccine is administered before the risk interval following dose 2 is complete, the risk interval will be truncated at the time of dose 3, and FU after dose 3 will be excluded from the dose 2 estimation. In this situation, for the dose 3 comparative risk estimation, the risk interval will start on the date of the third vaccine dose and will extend for the duration of the risk interval for dose 3.

For comparative analysis of outcomes identified separately in dose 1, dose 2, and dose 3 cohorts, comparative risks will be estimated separately by dose number. If comparative risk estimates are similar for dose 1, dose 2, and dose 3, then data from the dose 1 exposed/dose 1 unexposed cohorts, the dose 2 exposed/dose 2 unexposed cohorts, and the dose 3 exposed/dose 3 unexposed cohorts will be combined to obtain comparative risk estimates associated with at least 1 dose of the vaccine.

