A study design-related limitation is that any uncertainty regarding risk periods will lead to misclassification and attenuation of risk estimates. Sensitivity analyses with alternative risk intervals will be considered for outcomes for which the risk interval is not well characterized.

A limitation of the cohort design with concurrent unexposed comparators is the potential for residual or unmeasured confounding because it is unlikely that the data sources will have information on all potential confounders. To address potential confounding and potential misclassification of unexposed status, the SCRI, which automatically adjusts for time-invariant confounders, will be used as a secondary approach where feasible. However, the SCRI is not well suited to study outcomes with gradual onset, long risk intervals, or risk periods that are not well characterized.

A limitation specific to the cohort design with concurrent unexposed comparators is that unvaccinated individuals may become exposed to COVID-19 vaccine at any time during the study; if this situation occurs frequently, the amount of unexposed person-time in the unexposed comparator group will be reduced substantially, which will limit the precision of comparative risk estimates and could potentially lead to substantial imbalances in seasonality between exposed individuals and unexposed individuals, particularly for outcomes with long risk intervals. In primary series analyses, forming separate exposed cohorts by dose number and matching unexposed to exposed at the time of each vaccine will minimize the loss of unexposed person-time due to receipt of vaccine in these individuals between the first and second doses. Additionally, the sensitivity analyses with the historical unexposed comparator cohort for pregnancy and birth outcomes and the SCRI design will not be subject to this limitation. However, it is anticipated that even with separate matching of doses that FU time will be substantially longer in analyses of vaccine-associated enhanced respiratory disease in individuals in the vaccinated cohorts than in the unvaccinated comparator cohorts, since the risk interval is 365 days long. Further, the SCRI design and historical unexposed comparator cohort design are not feasible to be used to study this outcome.

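### Risk windows drawn around clusters in the study's own event timing inflate the RR then estimated in them, and the ordinary 95% CI does not allow for the search

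*Protocol*

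**What the plan says.** Protocol Section 8.7.3.6 treats two cases differently.

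- **Myocarditis/pericarditis.** The alternatives are fixed in advance: "Sensitivity analysis of myocarditis/pericarditis will be conducted using alternative risk interval definitions of 1-7 and 1-14 days".
- **Other events with poorly characterized intervals** (the list is left to the SAP). First, "descriptive analyses of the timing of events relative to vaccination will be conducted". Then: "If they are identified, temporal clusters will be used to define alternative risk intervals that will be used in sensitivity analyses".

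Comparative estimates for general safety events are specified in Section 8.7.2.2: "Cox models or Poisson regression will be used to estimate RRs and 95% CIs within the matched cohorts". Neither section gives the cluster-defined window a different estimator. Neither names held-out or external data for finding the cluster, or limits the result to descriptive use.

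**The concern.** A Cox or Poisson RR with an ordinary 95% CI assumes that the window was fixed independently of the events counted in it. Here the window is picked because vaccinated cases pile up there. Under no effect, chance clumping alone makes the exposed count in that window too high, while the comparator count in the same window is not selected. The ratio is biased upward, and the CI ignores the search.

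These analyses are meant to show whether a long window has diluted a real risk. An RR that exceeds 1 by construction cannot answer that question. The protocol's discussion of uncertain risk periods (Sections 8.7.3.6 and 8.9) mentions only attenuation, so a reader is not warned of bias in the other direction.

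**Working it through.** **1. Check of the event-count model against the plan's own figure.** Section 8.5 states its assumptions: "Assuming a matching ratio of 1:1 for analysis of the primary series" and, for doses, "under the assumption that each individual will receive 2 doses". With N vaccinated:

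- E0 = 2 × N × (days/365.25) × rate; E1 = RR × E0
- SE(ln RR) = √(1/E0 + 1/E1)
- Probability = Φ(ln(threshold/RR)/SE − 1.96)

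For myocarditis/pericarditis (5,000,000 vaccinated, 10 per 100,000 person-years, 21 days, RR 1.4, threshold 2.5): E0 = 57.5, E1 = 80.5, SE = 0.173, and Φ(0.580/0.173 − 1.96) = 0.919. The protocol states 92%, so the model reproduces it.

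**2. Event counts for illustration.** Section 8.5 gives 42-day windows and rates of 1.68 (Guillain-Barré syndrome, GBS) and 25.2 (Bell's palsy) per 100,000 person-years. Expected events per arm, two doses:

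- GBS, 5,000,000: 2 × 5,000,000 × 42/365.25 × 1.68/100,000 = 19.3
- GBS, 20,000,000: 77.3
- Bell's palsy, 5,000,000: 290

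One dose halves these to about 10, 39 and 145; Bell's palsy at 1,000,000 gives 29 per dose.

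**3. Null simulation (true RR = 1), two-dose counts, 20,000 runs each.** Daily Poisson events were spread evenly over days 1-42, with a 1:1 ratio. The cluster is the window of 2-21 days that maximizes c·ln(c/E) + (N−c)·ln((N−c)/(N−E)) in exposed events. Here N is the exposed total, c the count in the window and E = N × length/42. The RR is exposed over unexposed events in that window, with CI ln RR ± 1.96·√(1/e1 + 1/e0), adding 0.5 to both counts if either is zero. Each cell shows pooled RR; CI coverage of 1; share with lower limit above 1 (nominal 2.5%).

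| Events per arm | Best window always used | Only clusters passing a 5% scan test |
|---|---|---|
| 19.3 | 2.31; 93%; 6.6% | 2.57; 77%; 23% |
| 77.3 | 1.64; 78%; 22% | 1.88; 43%; 57% |
| 290 | 1.32; 72%; 28% | 1.42; 41%; 59% |

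The fixed 1-42 day window gave RR 1.00 and coverage 95-96%.

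**4. Same exercise with one-dose counts, windows of 3-21 days.** With the best window always used:

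| Events per arm | Median RR | Lower limit above 1 |
|---|---|---|
| 10 | 3.0 | 2.4% |
| 29 | 2.2 | 11% |
| 39 | 2.0 | 15% |
| 145 | 1.50 | 24% |

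Across repeats the last column spans about 2-26%. Among clusters passing a 5% scan test, the null median RR is about 1.5-4.0 and the lower limit exceeds 1 in about 8-58%.

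**5. Overall false-signal rate if a 5% scan test is required.** Multiply the two steps: 5% × 8% = 0.4% and 5% × 58% = 2.9%. With the two-dose counts: 5% × 23% = 1.2% and 5% × 59% = 3.0%. These are near or below 2.5%.

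**6. Does separating the steps work?** When the exposed events used for estimation are independent of those used to find the window, the pooled RR is 0.97-1.01. Coverage is 94-99%, and the lower limit exceeds 1 in 0.4-3.6%. Choosing in one random half and estimating in the other (one-dose counts) gave 0-1.8%.

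**The case against.** The strongest reply is that the rule is conditional on a cluster being identified, and that identification may be left to the SAP. This partly stands. A reader might infer from the 24-28% figures that the plan will raise false signals about ten times too often. The documents do not support that, because those figures take a best window in every null study. Under a formal 5% test the overall rate is about nominal. What remains is inflation of the RR and a CI that is too optimistic once a cluster is declared.

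It is also fair that same-data use is inferred. However, the only timing analysis named is this study's own, and the footnote to Section 5 has the monitoring, interim and final analyses each use the most recent data, with no separation stated. At that point Section 8.7.3.6 defers only the list of events to the SAP. The sequence from cluster to window to sensitivity analysis is stated as what will be done.

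Other stronger readings also go beyond the text:

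- **The CI always fails.** At about 10 events with no formal test, the lower limit exceeds 1 in 2.4%, which is nominal. At 19 events coverage is 93%. There the inflated estimate is the main harm.
- **The problem repeats over many outcomes, doses and subcohorts.** Section 8.7.3.6 names none, and GBS and Bell's palsy are not listed as poorly characterized.
- **The self-controlled risk interval (SCRI) analysis is also affected.** With an assumed control interval of days 43-84, coverage would fall to 38-42% for any cluster and 10-19% for significant ones. But Section 8.7.3.2 leaves the SCRI outcomes to the SAP, and Section 8.9 calls the design poorly suited to such events. Section 8.7.3.2 does allow a washout for them, so use is possible but not established.
- **Section 8.9 repeats the rule.** It says "Sensitivity analyses with alternative risk intervals will be considered for outcomes for which the risk interval is not well characterized", with no mention of clusters, so it is not a second instance.

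**Conclusion.** The concern holds in a limited form. As written, Section 8.7.3.6 lets the data choose the window and does not stop the same data from supplying an ordinary RR and 95% CI in it. Under no effect, the RR in a declared cluster has a median of about 1.5-4.0 after a 5% scan test. Its lower limit exceeds 1 in about 8-58% of declared clusters, against 2.5%; the two-dose runs agree at 23-59%. If windows are taken without a formal test, the overall rate is about 2-26%, or 28% at the largest two-dose count.

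These sizes depend on the assumed window lengths and scan rule, on uniform event timing, and on two events used only for their rates. The direction of the bias does not depend on those choices. Only sensitivity analyses of events other than myocarditis/pericarditis are touched. The primary RRs use the fixed windows of Table 8, and the 1-7 and 1-14 day alternatives are prespecified. It is worth correcting, but it does not threaten the main results.

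**What to change.** Replace the last sentence of Section 8.7.3.6 with text to this effect:

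> A temporal cluster found in the study data will be reported with a scan-statistic p-value adjusted for the search over windows. Any RR for that window estimated from the same data will be labelled exploratory and shown without a conventional 95% CI. Where event counts allow, the window will be chosen in a random half of the matched sets (exposed individuals with their comparators), and the RR and 95% CI will be estimated only in the other half.

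The split should not be made by data research partner. Sections 8.4.3 and 8.4.4 give median ages of 67 at Humana and 36 at Optum, so a window found in one population would be tested in a very different one.

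The cost is one paragraph and minor programming. The downside is wider intervals, or no conventional CI, for these sensitivity analyses. Nothing else in the plan changes.
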